4.0 STUDY OVERVIEW

4.2 Study Approach

This protocol is designed to describe a Phase I single center, double blind study that will enroll 36 patients having a diagnosis of degenerative infrarenal abdominal aortic aneurysms measuring 35-50 mm. in diameter by Computed Tomographic imaging. The PI, [name] MD will be unblinded. Co-Investigators, nurse coordinators and study subjects will be blinded. At Month 24 post-study product infusion, subjects will have the option to be unblinded to their investigational product.

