3.3 Proposed Intended Use Statement

Allogeneic MSCs are a novel therapeutic option to suppress growth of small AAA. Human MSCs are intended for investigational use only by selected investigators familiar with their use and experienced in conducting clinical studies. Human MSCs may only be administered to human subjects participating in clinical studies sponsored/approved by Indiana University School of Medicine, and who have provided formal written consent.

3.4 Study Objectives.

The principal objective of this study is as follows:

Assess the safety and efficacy of administration of allogeneic MSCs in patients with small AAA.

This study will test the hypothesis that administration of MSCs in doses of 1×10^6 MSCs/kg. and 3×10^6 MSCs/kg demonstrate safety in patients with small AAA. This trial will also test the hypothesis that MSCs, in a dose dependent fashion (1×10^6 MSC/kg. vs. 3.0×10^6 MSC/kg.), promote the frequency and immune suppressor function of Treg cells and decrease AAA inflammation as measured by computed tomography. In an double blinded, Phase I trial, 36 patients with AAA measuring 35-50 mm in maximal transverse diameter (MTD) will be randomized in a 1:1:1 fashion to receive intra-venously either a single dose of 1×10^6 MSCs/kg., 3×10^6 MSCs/kg. , or placebo (Plasmalyte A) (n =12/group). The primary safety endpoints will be incidence of treatment related adverse events accrued over 24 months. Efficacy measures are changes in frequency and immune suppressor function of Tregs, number and cytotoxic activity of CD4+/CD8+ CD28- T-cells, activated monocytes, and changes in aortic inflammation as measured by PET CT compared to baseline. Secondary endpoints measured out to year 5 will include changes in IL-10 and Tr1 levels. Duplex ultrasound measurements of the AAA, which is considered standard of care, will be recorded as change in aortic inflammation during long-term follow-up. Incidence of surgical intervention, aneurysm related death, quality of life, and major adverse cardiac events will be recorded through year five (5).

Completion of this study will determine if MSCs are safe in patients with AAA and provide critical insights that will direct a placebo-controlled, Phase II randomized trial.

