5.2.2 Duration of study activities

Enrollment is anticipated to continue for approximately 1–2 years. In the event that additional studies are going to be conducted, new protocols will be developed specifically for those studies.

5.3 Patient Selection. The eligibility criteria for prospective enrollment of subjects are shown in **Table 1**.

Table 1. Inclusion/Exclusion Criteria for Enrollment of Subjects

Inclusion criteria
	
 1. Be ≥ 40 and ≤85 years of age. 2. Have diagnosis of non-inflammatory degenerative infrarenal abdominal aortic aneurysms measuring 30-50mm. in diameter by Computed Tomography (CT) scan. 3. Females of childbearing potential must be willing to use one form of birth control for the duration of the study. Female participants must undergo a blood or urine pregnancy test at screening.

Exclusion criteria
	
 1. Inflammatory AAA defined by a thickened aortic wall and retroperitoneal fibrosis and adhesions of peritoneal organs, and elevated erythrocyte sedimentation rate or in the opinion of investigator. 2. Mycotic AAA defined as sacular morphology, a positive blood culture, fever, or in the opinion of the investigator. 3. Symptomatic, Saccular, or any AAA associated with thoracic aorta dilatation > 5.0 cm. 4. Infra-renal AAA associated with Marfan’s or Ehlers-Danlos Syndrome or other connective tissue disorders 5. Common or external iliac artery aneurysm > 30 mm. in maximal transverse diameter. 6. AAA due to dissection. 7. Allergy to iodine contrast. 8. History of untreated or recurrent cancer within the last 5 years, except basal cell skin carcinoma.

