	
 9. eGFR < 30mL/min. 10. Any condition requiring immunosuppressant medications (e.g., for treatment of organ transplants, psoriasis, Crohn’s disease, alopecia areata, rheumatoid arthritis, scleroderma, lupus). 11. Acute coronary syndrome in the last 30 days prior to enrollment. * 12. CHF hospitalization within the last 30 days prior to enrollment. * 13. HIV or HCV positive. 14. Contraindication to Computed Tomography or known allergy to contrast media. 15. Any bleeding diathesis defined as an INR ≥ 2.0 (off anticoagulation therapy) or history of platelet count less than 70,000 or hemophilia. 16. Pregnant or breast feeding women. 17. Significant hepatic dysfunction (ALT or AST greater than 2 times normal). 18. Life expectancy less than two years. 19. Inability to provide written informed consent due to cognitive or language barriers (interpreter permitted). 20. Presence of any clinical condition that in the opinion of the PI or the sponsor makes the patient not suitable to participate in the trial. 
*As defined by the standard definitions of CHF and ACS by the American Heart Association.

Participant Withdrawal Criteria	At the discretion of the investigator or at the request of the participant. The reason for withdrawal will be documented, specifically if the reason is due to an adverse event.

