6.1.4 Required training and MSC administration

MSCs will be manufactured at the Case Cancer Comprehensive Center Cellular Therapy Lab at Case Western Reserve University in Cleveland, Ohio with supervised and trained personnel. The MSCs, in the

appropriate dose, will be shipped to the Cell Therapy Laboratory at University Hospital where the MSCs will be thawed and diluted 1:1 with Plasmalyte A and administered within 4 hours of the thawing process. All personnel in the Stem Cell Laboratory are qualified in the processing on MSCs for patient administration. The thawed MSCs will then be administered to the patients in a monitored setting with telemetry and pulse oximetry.

MSC Administration. This is a randomized, double blinded trial and after enrollment, patients will be randomized in a 1:1:1 fashion to receive placebo (Plasmalyte A), 1×10^6 MSC/kg., or 3×10^6 MSC/kg. The rationale for selection of these doses was presented in the Research Strategy. IV MSC infusions will occur in a monitored inpatient room on the Surgical Intensive Care Unit at the Roudebush VA Hospital or the Clinical Research Center at IU Health University Hospital. Patients will be pre-medicated with hydrocortisone (25-50 mg. IV) and diphenhydramine (Benadryl, 25-50 mg. IV). All subjects will be monitored throughout the MSC infusion procedure with vital signs and pulse oximetry beginning 15 minutes prior to infusion and ending 2 hours post procedure. They will also be evaluated for clinical signs of pulmonary distress including progressive or sustained hypoxia, dyspnea, and tachycardia. If enrolled patients develop any of the following conditions within 24 hours of planned infusion, MSC delivery will be halted:

- a. Fever (Temperature increase to $\geq 100.4^\circ\text{F}$)
- b. Upper respiratory tract infection diagnosed by independent health provider.
- c. Significant shortness of breath
- d. Unanticipated change in consciousness or neurological change
- e. Major adverse cardiac event

All patients will be admitted for continued observation to the SICU at the Roudebush VA Hospital or the Clinical Research Center at IU Health University Hospital. The patient will be observed for two hours after the study product infusion and then discharged home. The patient will be re-examined on Days 7 and 14 for treatment related adverse events.

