7. STUDY PROCEDURES

7.1 Workflow

MSC preparation. Donor infectious disease testing will be performed by CLIA certified Laboratories. Allogeneic donor Infectious Diseases testing will include anti-HIV-1/2 and anti-HCV. Testing will be repeated if it exceeds 30 days. Potential donors whose testing is incomplete or not available within 30 days will not be eligible to donate bone marrow and testing will be repeated to confirm ID markers. Potential donors testing positive for any of these infectious diseases will NOT be eligible.

Randomization Scheme and MSC Dosing. The PI, [name] MD., will determine inclusion in the study. After that decision has been rendered, the patient will be screened for enrollment. After enrollment, 36 patients will be randomized to receive MSCs or placebo IV through an antecubital vein (**Figure 1**).

Serum samples will be collected pre-MSD administration, 1 and 6 months' post MSC-treatment and analyzed in the Cellular Therapy Laboratory of University Hospital to determine if patients develop antibodies against allogeneic MSCs.

Baseline Screening and Follow-Up Schedule. The following evaluations will be carried out at baseline to determine if patient is eligible for study: (1) Baseline blood tests (complete blood count, serum chemistries and liver panel); (2) infectious disease panel and HLA typing; (3) medical history and physical exam; (4) concomitant medications; (5) pregnancy test for women of childbearing age ;(6)12 lead ECG; (7) 18-fluorodeoxyglucose (FDG) uptake with positron emission tomography/computed tomography (PET/CT) will be performed at baseline and Day 14. Computed tomographic angiography of the abdominal aorta and iliac arteries (as part of "Standard of Care") will be performed at month 12. Duplex ultrasound of the aorta will be performed at month 12 while the patients are enrolled in the trial to monitor AAA size. Follow up studies are detailed in **Table 2**, below. Subjects will return for long-term follow-up visits at six month intervals from year 1 (+/- 4 weeks) through year 5 (+/- 4 weeks). Window ranges for follow-up visits are guidelines for scheduling and will not be considered a protocol deviation if visits fall outside of these ranges. See **Table 3**, below, for details on the long-term follow-up visits.

- Annual CT abdominal exams beginning at year 1 are considered Standard of Care.

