9.1 Bias Minimization

All subjects meeting the specified eligibility criteria will be enrolled on a first-come basis.

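### The PI is unblinded without a stated reason, and the plan does not give the relatedness judgement behind the primary safety endpoint to a blinded person

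*Combined protocol and SAP*

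**What the plan says.** **Who is blinded.** The synopsis and sections 2, 3.4, 4.2 and 6.1.4 call the trial double blind or double blinded. Section 4.2 then states: "MD will be unblinded. Co-Investigators, nurse coordinators and study subjects will be blinded". The first clause refers to the PI. No reason is given there or elsewhere in the available text.

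**What the endpoint is.** Section 3.4: "The primary safety endpoints will be incidence of treatment related adverse events accrued over 24 months". Section 9 likewise measures safety by treatment-related events.

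**Who judges events.** Section 6.1.4: "The patient will be re-examined on Days 7 and 14 for treatment related adverse events". No examiner is named. Section 10.1 has the Investigator document events and judge seriousness, without saying which investigator or whether that person is blinded. It names no one for relatedness. Table 2 schedules adverse event evaluations at each visit, also without an assessor.

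**What the PI does.** Section 12.2 makes the PI responsible for seeing that all CRFs are completed, reviewed and approved, and finally responsible for the accuracy of their data; an authorized staff member may sign. Under the stopping rules in 10.1, the PI takes part in determining the etiology of each stopping event, but the boards decide on halting or resuming independently of the PI. In section 7.1 the PI "will determine inclusion in the study. After that decision has been rendered, the patient will be screened for enrollment". Exclusion criterion 20 (section 5.3, Table 1) covers "Presence of any clinical condition that in the opinion of the PI or the sponsor makes the patient not suitable".

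**Safeguards.** Section 9.1, on bias minimization, says in full: "All subjects meeting the specified eligibility criteria will be enrolled on a first-come basis".

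**The concern.** An endpoint limited to treatment-related events depends on attribution. Blinding protects such an endpoint only if the person attributing cause does not know the arm. Here the one investigator who does know the arm has final responsibility for the recorded data, and the attributing person is unidentified. Section 9 notes that four previous trials reported no adverse events with MSC treatment, so the count of related events may be very low and a few calls could make up the whole endpoint. Bias could run either way: knowing that a patient had cells could prompt more attribution or less. The result is meant to show whether MSCs are safe and to direct a Phase II trial (3.4).

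A secondary exposure is eligibility. An unblinded person who decides inclusion, partly on opinion, could act on a predicted allocation. This matters only if upcoming allocations can be foreseen. The available text describes neither sequence generation nor concealment, so it does not rule that out.

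**Working it through.** **1. Text check.** The claim rests on no planned sample size or power figure, so there is none to reproduce. Setting the relevant sections side by side:

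| Task | Who does it | Stated to be blinded? |
|---|---|---|
| Re-examination, Days 7 and 14 (6.1.4) | not named | no |
| Documenting events, judging seriousness (10.1) | the Investigator | not stated |
| Judging relatedness (3.4, 9, 10.1) | not named | no |
| Etiology of stopping events (10.1) | PI, study coordinator, monitoring board, specialists | PI is not |
| Final responsibility for CRF data (12.2) | PI | no |
| Inclusion (7.1) | PI | no |

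No row ties the relatedness judgement to a blinded person.

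**2. Sensitivity to one call.** Inputs: 12 patients per group (3.4); Wilson 95% intervals (section 9); z = 1.96, so z² = 3.8415. Section 9 speaks of differences between routes of delivery. This trial has one route, so I take the comparison to be between arms.

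The Wilson interval has centre (p + z²/2n)/(1 + z²/n) and half-width z·√[p(1−p)/n + z²/4n²]/(1 + z²/n).

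- 0/12: lower limit 0; upper limit z²/(n + z²) = 3.8415/15.8415 = 24.2%.
- 1/12 = 8.3%: centre 0.2434/1.3201 = 18.4%, half-width 0.2238/1.3201 = 17.0%, giving 1.5 to 35.4%.
- 0/24: 0 to 3.8415/27.8415 = 13.8%.
- 1/24 = 4.2%: centre 0.1217/1.1601 = 10.5%, half-width 0.1131/1.1601 = 9.8%, giving 0.7 to 20.2%.

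**3. Difference from placebo.** The Newcombe interval built on the Wilson limits has lower limit d − √[(p₁−l₁)² + (u₂−p₂)²] and upper limit d + √[(u₁−p₁)² + (p₂−l₂)²], with placebo at 0/12.

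- One dose arm, 1/12 v 0/12: d = 8.3; lower 8.3 − √(6.8² + 24.2²) = −16.9; upper 35.4.
- Both MSC arms pooled, 1/24 v 0/12: d = 4.2; lower 4.2 − √(3.4² + 24.2²) = −20.3; upper 20.2.

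One call moves the estimate visibly, but both intervals still include zero widely. These figures measure how sensitive the endpoint is. They do not estimate bias.

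**The case against.** The strongest reply is that the harm is inferred. A reader might conclude that an unblinded PI rates relatedness, or that the safety result is already biased. The documents support neither. No section gives the PI the relatedness call, and the Investigator in 10.1 could be one of the blinded co-investigators. Responsibility for CRF accuracy is not authority to re-rate causality, and another staff member may sign. Figure 1 and the text between the stopping rules and section 11 were not available, so absence is established only for the rest. All this stands. What remains is that the assessor and that person's blinding are unassigned.

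A reader might also infer that the PI can steer patients towards arms. The documents do not show that either. Inclusion precedes randomization, section 9.1 enrols all eligible patients as they come, and nothing gives the PI the allocation list. Other patients may be randomized between a PI decision and that patient's own allocation. The mycotic criterion, "Mycotic AAA defined as sacular morphology, a positive blood culture, fever, or in the opinion of the investigator", may be applied by a blinded co-investigator. Eligibility is therefore the lesser point.

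The PI may need to know the arm: two stopping rules count events in the MSC group, and positive product cultures are reported to the PI. That is plausible, but the plan does not give it as the reason, and neither task requires the same person to decide eligibility or influence attribution.

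Finally, MACE and surgical intervention are recorded without a relatedness test (3.4, 10.1), so not every safety outcome is exposed, and section 9 uses its intervals only as description. Both limit the consequence. The primary endpoint itself still depends on attribution.

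**Conclusion.** The point holds in limited form and should be fixed. The plan states that the PI is unblinded, gives no reason, and does not place the relatedness judgement with a blinded person, although blinded co-investigators already exist. One call is worth 8.3 percentage points in a single arm or 4.2 points in the pooled MSC group, which does not settle a safety conclusion on its own. The difference intervals assume no related events on placebo and a comparison between arms. Bias is not shown, and the absence of a named blinded assessor is a statement about the available text only. The eligibility exposure is secondary and depends on allocations being foreseeable, on which the text is silent.

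**What to change.** 1. **Section 10.1:** have a blinded co-investigator rate seriousness, severity and relatedness to the study infusion, without delaying immediate SAE reporting. Those applying the stopping rules add the arm afterwards. **Section 12.2:** state that the PI's CRF review may query that rating but not change it.
2. **Section 9:** report all adverse events by arm regardless of attribution, beside the related events. Reconcile this with the sentence in 10.1 under which events in the enrollment period are neither collected nor analysed unless serious; otherwise the table would hold only serious events for that period.
3. **Section 7.1 and criterion 20:** have a blinded co-investigator make the opinion-based eligibility decision. State that the allocation list is held by someone who does not recruit, decide eligibility, rate events or run study assays. The product laboratory is not an obvious holder. MSCs are "shipped to the Cell Therapy Laboratory at University Hospital where the MSCs will be thawed and diluted 1:1 with Plasmalyte A", and section 7.1 has what appears to be the same laboratory test patient serum for antibodies against the cells.
4. **Section 4.2:** give the reason the PI is unblinded, or qualify the double-blind label wherever it appears.

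The cost is protocol wording, one extra table and some extra work for the blinded co-investigators. The documents do not give their number or duties, so the amount cannot be stated. The PI gives up the rating and the opinion-based eligibility decisions. The stopping rules are unchanged.

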4.3 Study Duration

It is expected that the study will be completed within 8 years. Each patient will be followed for 24 months for assessment of safety with long-term follow-up through year 5 after enrollment.

5. STUDY POPULATION

5.1 Sample Size and Target Study Population

5.1.1 Sample size

The total number of individual subjects is expected to reach up to 36.

5.1.2 Study population

The study population will be representative of adults at least 40 years of age and at most 85 years of age with small (30-50mm) AAA. Children will not be eligible for this study because AAA is a degenerative and inflammatory disease of the aged. It is anticipated that at minimum, enrollment will reach approximately 1-16 qualifying adults per month for 1–2 years.

5.1.3 Alignment with intended study population

The study population includes patients likely to benefit from allogeneic MSC transplantation. It will also include other patients who will be controls.

5.2 Recruitment Methods

5.2.1 Recruitment for Study

Eligible patients will be invited to participate in the study on a first-come basis, subject to Indiana University School of Medicine weekly recruitment goals. Patients will be recruited for this study from the Richard Roudebush VA Medical Center and IU Health Methodist Hospital. Patients will be informed of the possible risks of the procedure and will be required to give informed consent before study-specific procedures can proceed. A minimal financial inducement will not be offered. Each subject will be informed that no personally relevant clinical information will be derived from the collected data, and that the only possible benefit to the subject is a decrease in AAA expansion rates. Medications will be documented and certain medications may be held. Each subject’s involvement in the study will be limited to the period between signing of the informed consent form (ICF) and the completion of study specific procedures.

5.2.2 Duration of study activities

Enrollment is anticipated to continue for approximately 1–2 years. In the event that additional studies are going to be conducted, new protocols will be developed specifically for those studies.

5.3 Patient Selection. The eligibility criteria for prospective enrollment of subjects are shown in **Table 1**.

Table 1. Inclusion/Exclusion Criteria for Enrollment of Subjects

Inclusion criteria
	
 1. Be ≥ 40 and ≤85 years of age. 2. Have diagnosis of non-inflammatory degenerative infrarenal abdominal aortic aneurysms measuring 30-50mm. in diameter by Computed Tomography (CT) scan. 3. Females of childbearing potential must be willing to use one form of birth control for the duration of the study. Female participants must undergo a blood or urine pregnancy test at screening.

Exclusion criteria
	
 1. Inflammatory AAA defined by a thickened aortic wall and retroperitoneal fibrosis and adhesions of peritoneal organs, and elevated erythrocyte sedimentation rate or in the opinion of investigator. 2. Mycotic AAA defined as sacular morphology, a positive blood culture, fever, or in the opinion of the investigator. 3. Symptomatic, Saccular, or any AAA associated with thoracic aorta dilatation > 5.0 cm. 4. Infra-renal AAA associated with Marfan’s or Ehlers-Danlos Syndrome or other connective tissue disorders 5. Common or external iliac artery aneurysm > 30 mm. in maximal transverse diameter. 6. AAA due to dissection. 7. Allergy to iodine contrast. 8. History of untreated or recurrent cancer within the last 5 years, except basal cell skin carcinoma.

	
 9. eGFR < 30mL/min. 10. Any condition requiring immunosuppressant medications (e.g., for treatment of organ transplants, psoriasis, Crohn’s disease, alopecia areata, rheumatoid arthritis, scleroderma, lupus). 11. Acute coronary syndrome in the last 30 days prior to enrollment. * 12. CHF hospitalization within the last 30 days prior to enrollment. * 13. HIV or HCV positive. 14. Contraindication to Computed Tomography or known allergy to contrast media. 15. Any bleeding diathesis defined as an INR ≥ 2.0 (off anticoagulation therapy) or history of platelet count less than 70,000 or hemophilia. 16. Pregnant or breast feeding women. 17. Significant hepatic dysfunction (ALT or AST greater than 2 times normal). 18. Life expectancy less than two years. 19. Inability to provide written informed consent due to cognitive or language barriers (interpreter permitted). 20. Presence of any clinical condition that in the opinion of the PI or the sponsor makes the patient not suitable to participate in the trial. 
*As defined by the standard definitions of CHF and ACS by the American Heart Association.

Participant Withdrawal Criteria	At the discretion of the investigator or at the request of the participant. The reason for withdrawal will be documented, specifically if the reason is due to an adverse event.

